All eligible participants will be scheduled for assessments at two time points: pre (baseline) and post intervention (12-weeks). The assessments consist of a battery of 8-10 questionnaires taking about 20-30 minutes to complete. Next, physiological measurements will be conducted by a trained research assistant and will take about 10 minutes to complete. Participants will receive \$30 for completing each assessments. Completed questionnaires will be coded with a study ID to protect confidentiality. All personal health information will be entered into a password protected secure server environment within UCSD-HSRC. After the baseline assessment, participants will be randomized to either the Hatha Yoga Intervention or to the Restorative Yoga Intervention. Randomization will occur through a web portal linked to a secure file providing block randomized digits that was prepared by the study statistician. There will be one block file for each site, with 30 digits in each file, allowing each site to have a balanced randomization. Research staff will not have access to the randomization file. Participants will be told of their group assignment and will be allowed to ask additional questions at that time.

Assessment Questionnaires and Measurements:

Screening: Medical record information will be used by screening physicians to complete the Back Pain History Questionnaire which will allow the investigators to assign a descriptive diagnosis based on the Quebec Nomenclature on Activity Related Spinal Disorders¹⁰⁴. The measure has been used in previous VA studies¹⁰⁵⁻¹⁰⁷. Additional information on co-morbid diagnoses, opioid pain medication usage, and ongoing treatments will also be collected including information on TBI, PTSD and other psychological diagnoses, and substance use.

Demographics: A brief questionnaire will assess age, gender, education, race/ethnicity, employment status, military rank and duties, and combat status.

Pain interference with daily function and pain severity will be measured with the short version of the Brief Pain Inventory (BPI).¹⁰⁸ Pain interference will serve as the primary outcome. The BPI has been validated with CLBP.¹⁰⁹ The pain interference score is the mean of the 7 interference items. The pain severity score is the mean of 4 severity items. The BPI has good reliability (alpha 0.77 - 0.91).

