Statistical Management and Analysis: Qualitative data will be managed and analyzed by Co-I [name]. Results will be presented to the research team and additional sub-analyses will be conducted as needed before the intervention is modified. Health outcome data and mediational variables will be collected directly before and after the 12-week yoga program using physiological assessments and questionnaires. We will assess the effect size of the difference in change in health outcomes (pain interference, pain severity, and physical functioning) from pre- to post-intervention between

intervention groups using a linear random effects model. We will assess clustering by site with a likelihood ratio test. The point estimate of difference in change score between two groups and the 95% confidence interval for the estimated difference will be provided. We will also perform multivariate analysis and an adjusted effects size (with 95% CI) by including baseline characteristics that are significantly imbalanced between two groups as covariates in the random effects model. Analyses will be conducted by the biostatistician ([name]). The effect size estimates (and CI width) will help inform power calculations for the subsequent R01 submission. R software packages will be used for all statistical analyses.

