17. POTENTIAL BENEFITS

The primary purpose of the study is to examine feasibility of yoga research and refinement of a yoga intervention for active-duty military personnel. Thus, no direct benefit to participants is anticipated. Yoga has been shown to improve health outcomes in other populations with CLBP/CNP, and may help some individuals, but our study is not powered to make scientific conclusions regarding efficacy. Results of the study will provide important information that will prepare study investigators to conduct a full-scale randomized controlled trial of yoga for military personnel with CLBP/CNP.

The results of this study will provide essential information for medical and mental health professionals who treat veteran and active-duty US military regarding the dimensions of yoga perceived as most helpful and well-received for different conditions, and will guide future research asking specific questions regarding efficacy and effectiveness of specific interventions.

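### The main effect size is a difference in change scores; the outcome's own baseline score should always be a covariate

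*Combined protocol and SAP*

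**What the plan says.** Section 9, under Statistical Management and Analysis, covers pain interference, pain severity and physical functioning. The target is set by "We will assess the effect size of the difference in change in health outcomes" from before to after the programme, compared between "intervention groups using a linear random effects model". The reported result follows: "The point estimate of difference in change score between two groups and the 95% confidence interval for the estimated difference will be provided". The plan does not list the model's fixed effects, say whether the response is the change score or both time points, or say how baseline is handled.

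A second, adjusted effect size with its own 95% CI comes from "including baseline characteristics that are significantly imbalanced between two groups as covariates in the random effects model". Neither the test nor its level is given, and the plan does not say whether the outcome's own baseline score counts as such a characteristic. No other section makes that score a fixed covariate, constrains the arms' baseline means to be equal, or names any covariate in advance.

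Assessments are at baseline and week 12 only, and randomisation is blocked by site, with no stratification on baseline pain (Section 9, Assessments and Randomization). On the use of the results: "The effect size estimates (and CI width) will help inform power calculations for the subsequent R01 submission". This is Aim 6. Section 17 adds that "our study is not powered to make scientific conclusions regarding efficacy".

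**The concern.** A change-score comparison fixes the coefficient of the baseline score at 1, whatever the data show. Two things follow when the true slope of the week-12 score on baseline is below 1. The estimate carries more noise than necessary. And if one arm happens to start worse, regression to the mean makes that arm appear to improve more.

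Adjusting only after a significant imbalance test does not repair this. With about 25 per arm the test flags only large differences, and the decision to adjust then depends on the data. Precision matters here because the CI width is itself an input to planning the next trial.

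**Working it through.** **Inputs from the documents.** N = 50 randomised (Sections 9, 10 and 20), so 25 per arm assuming 1:1; two time points; two-sided 95% CI. Section 5 gives 60 instead, and the randomisation files hold 30 entries per site; N = 60 is noted in steps 3 and 5.

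**Assumptions.** The documents give no pre-post correlation ρ, no SDs and no level for the imbalance test. I take ρ from 0.4 to 0.9, SD ratio k = SD_post/SD_pre of 0.8, 1 or 1.25, and p<0.05. Data are bivariate normal with no dropout and no clustering. The plan states no expected CI width or power, so there is no figure of its own to reproduce.

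**1. Does the random effects model already adjust?** Not by itself. In one simulated data set with two time points, a random-intercept model gave a group × time term of -0.1711, equal to the raw difference in change. Adding a baseline covariate as a main effect left it at -0.1711. Regressing the later score on arm and baseline (ANCOVA) gave -0.217, with SE 0.215 against 0.281.

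**2. Variance per participant, in units of SD_pre².**
- Change score: 1 + k² − 2ρk
- ANCOVA: k²(1 − ρ²)
- Difference: (1 − ρk)²

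The difference is never negative and is zero only when the slope ρk is 1. With k = 1 the ratio of ANCOVA to change-score variance is (1 + ρ)/2.

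**3. CI half-width, k = 1.** Worked at ρ = 0.5:
- Change: t(48) × √(2(1 − 0.5) × 2/25) = 2.0106 × 0.283 = 0.569 SD
- ANCOVA: t(47) × √(0.75 × 2/25 × (1 + 1/46)) = 0.498 SD

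Simulated means (40,000 trials per row; narrowing from unrounded values):

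| ρ | Change | ANCOVA | Narrowing |
|---|---|---|---|
| 0.4 | 0.62 | 0.52 | 15.3% |
| 0.5 | 0.57 | 0.50 | 12.4% |
| 0.6 | 0.51 | 0.46 | 9.5% |
| 0.7 | 0.44 | 0.41 | 6.7% |
| 0.8 | 0.36 | 0.34 | 4.0% |
| 0.9 | 0.253 | 0.249 | 1.4% |

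In a single trial the adjusted interval is the narrower one in 98% of cases at ρ = 0.5, 91% at 0.7 and 58% at 0.9. At ρ = 0.5 a change-score analysis needs 50/0.75 ≈ 67 participants to match ANCOVA with 50. With N = 60 the half-widths at ρ = 0.5 are 0.52 and 0.45.

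**4. Unequal SDs, ρ from 0.4 to 0.7.** Narrowing runs from 25.8% to 19.8% at k = 0.8, and from 7.3% to −0.2% at k = 1.25. At ρ = 0.8 and k = 1.25 the slope is 1 and adjusting widens the interval by 1.1% on average.

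**5. Chance imbalance, ρ = 0.5, k = 1.**
- A baseline difference d shifts the change estimate by (1 − ρk)d in size: 0.15 SD for d = 0.3 and 0.20 SD for d = 0.4.
- The test fires at |d| above about 2.0106 × √(2/25) = 0.569 SD (0.52 SD with 30 per arm).
- |d| exceeds 0.3 SD in 28.9% of trials and 0.4 SD in 15.7%. The test fires in about 5% of trials, so it misses about 1 − 0.05/0.289 = 83% and 1 − 0.05/0.157 = 68% of these. Simulation gives 82.8% and 68.4%.
- For d between 0.35 and 0.45 SD, mean error is −0.198 (change), −0.197 (adjust if significant) and +0.001 (always adjust).
- Over all trials the SD of the estimate is 0.283, 0.274 and 0.247 respectively. Adjusting only if significant recovers (0.283 − 0.274)/(0.283 − 0.247), about a quarter of the gain.
- For d between 0.45 and 0.55 SD, which is about 6% of trials, 95% CI coverage is 89%, 90% and 95%.

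**The case against.** The strongest reply is that nothing planned is invalid. Over all randomisations at ρ = 0.5, coverage is 95.0% for the change score, 95.6% for adjusting if significant and 95.0% for ANCOVA. The low coverage above belongs to a narrow band of imbalances. In that band change-score coverage rises to 91%, 93% and 94% at ρ of 0.7, 0.8 and 0.9. The study is a pilot that only estimates, and a half-width of 0.50 SD is still too wide to settle an effect size. All this stands, and it limits the point to efficiency and conditional bias.

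The adjust-if-significant simulation also simplifies the plan, which would report both estimates and would add covariates to a random effects model rather than switch to ANCOVA. That is fair, but it does not help the plan: by step 1, a triggered main-effect covariate may adjust nothing when both times are responses. Likewise, if outcome baselines do not count as baseline characteristics, they never enter at all. The wording could accommodate a constrained-baseline model, which would meet the concern, but the plan does not specify one.

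The gain depends on an unknown correlation and nearly vanishes when the slope is close to 1. At slope exactly 1 the adjusted interval is wider in 80% of trials, by 4.6% at the 95th percentile and 7.7% at the 99th; the 1% is only the average. The absolute half-widths are idealised for both methods, because dropout and class clustering are left out.

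The choice can still matter for the next trial. For an illustrative 0.5 SD effect at 80% power and two-sided 5%, with ρ = 0.5, planning on the change-score SD gives 63 per arm and on the baseline-adjusted SD 48.

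**Conclusion.** The concern holds. The main estimate leaves the outcome's baseline out as a covariate, and the rule for the second estimate would bring it in for only about 5% of trials if the test is at p<0.05. For correlations of 0.4 to 0.7 and equal SDs, always adjusting narrows the 95% CI by about 15% to 7% on average and removes the shift from chance imbalance. The gain is larger if the SD falls after treatment and close to nil if the slope is near 1. These sizes rest on the assumed correlation, SD ratio, test level and 25 per arm; N = 60 does not change the conclusion. The planned estimate remains valid, so this is a change the plan should make for efficiency.

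**What to change.** For pain interference, pain severity and physical function, define the main estimate as the arm coefficient, with 95% CI, from a regression of the week-12 score on arm, that outcome's baseline score and site. Alternatively, specify the random effects model with both time points as responses and the arms' baseline means constrained equal. Do not add baseline only as a main effect to an unconstrained group × time model, since that leaves the estimate unchanged.

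State that the outcome's baseline score is included whatever its p-value, in place of the imbalance rule for that covariate. Show the raw difference in change descriptively.

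The cost is one or two sentences and one or two degrees of freedom, with no new data or visits. In the range examined, the worst average result is an interval about 1% wider, when the slope is 1.

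### The adjusted effect size picks covariates by significant baseline imbalance between randomised arms, so chance decides the adjustment and almost all of the gain from adjusting for baseline is forgone

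*Combined protocol and SAP*

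**What the plan says.** Section 9, Statistical Management and Analysis, compares pre-to-post change between arms with a linear random effects model: "The point estimate of difference in change score between two groups and the 95% confidence interval for the estimated difference will be provided". It then adds: "We will also perform multivariate analysis and an adjusted effects size (with 95% CI"), obtained by "including baseline characteristics that are significantly imbalanced between two groups as covariates in the random effects model". The section names no candidate variables, test or significance level, and no prognostic criterion. It does not say how a covariate enters the model. On site it says: "We will assess clustering by site with a likelihood ratio test".

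Section 9, Assessments and Randomization, places allocation after the baseline assessment, with one block file per site: "Randomization will occur through a web portal linked to a secure file providing block randomized digits that was prepared by the study statistician".

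The pool of baseline variables is large. One item alone reads "A brief questionnaire will assess age, gender, education, race/ethnicity, employment status, military rank and duties, and combat status", and the same part of Section 9 lists pain, disability, mood, quality-of-life, fatigue and physical measures.

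On use of the results: "The effect size estimates (and CI width) will help inform power calculations for the subsequent R01 submission". Section 17 adds that "our study is not powered to make scientific conclusions regarding efficacy".

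**The concern.** After proper randomisation, a baseline difference that reaches significance is a chance event. It carries no information about whether the variable predicts change in pain interference. The rule therefore admits variables on the wrong criterion, and leaves out a strong predictor whenever its imbalance falls short of significance.

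Two things are at stake, both modest. Precision available from adjusting for a variable known to matter, above all the outcome's own baseline score, is used only when chance happens to unbalance it. And Aim 6 seeks effect sizes for planning a full trial, yet the CI width from a covariate set picked by chance does not describe an analysis that such a trial could prespecify. Section 9 does not say whether the adjusted or the unadjusted version is meant for that purpose.

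**Working it through.** The plan states no SD, correlation or power figure, so there is nothing to reproduce.

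**Inputs.** From the documents: two arms, 50 randomised (Section 9), hence about 25 per arm. The synopsis in Section 5 says 60, so 30 per arm is a sensitivity case. Assumed: imbalance test at two-sided 0.05, 20 candidate variables, all correlations, equal pre and post variances, normal data, no dropout. Every width below is a mean 95% CI width divided by that of the unadjusted change-score analysis, at 25 per arm, by simulation unless a formula is shown.

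**1. How often a variable enters.** By construction this is 5% for each variable, prognostic or not. The imbalance needed is t(0.975, 2n−2) × √(2/n): 0.569 SD at n = 25 and 0.517 SD at n = 30. The chance that at least one of 20 independent candidates enters is 1 − 0.95^20 = 64%. It is about 42–43% if the candidates are correlated 0.5 with one another.

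**2. The outcome's own baseline value.** With pre-post correlation r, the change score has variance 2σ²(1 − r). The 12-week score given baseline has variance σ²(1 − r²). The ratio is (1 + r)/2, so the width ratio is √((1 + r)/2).

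| r | Large-sample formula | Always adjusted | Adjusted only if imbalanced |
|---|---|---|---|
| 0.3 | 0.806 | 0.82 | 0.994 |
| 0.5 | 0.866 | 0.88 | 0.997 |
| 0.7 | 0.922 | 0.93 | 0.999 |

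A rough check of the last column at r = 0.5: 0.95 × 1 + 0.05 × 0.877 = 0.994. The simulated 0.997 is nearer 1 because an imbalanced covariate is collinear with arm. At 30 per arm, always adjusting gives 0.81 / 0.87 / 0.93.

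**3. One other covariate, apart from the baseline value.** The change score is the response, with 20 candidates at pairwise correlation 0.5, all equally correlated with change.

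| Correlation with change | Imbalance rule | One prespecified covariate | Prespecified ÷ rule |
|---|---|---|---|
| 0 | 1.03 | 1.01 | 0.98 |
| 0.1 | 1.03 | 1.01 | 0.98 |
| 0.2 | 1.02 | 0.99 | 0.97 |
| 0.3 | 1.01 | 0.96 | 0.96 |
| 0.4 | 0.99 | 0.93 | 0.94 |
| 0.5 | 0.96 | 0.88 | 0.91 |

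(Last column from unrounded widths.) With 20 independent non-prognostic candidates the rule gives 1.06. Coverage of the rule's CI ran from 94.6% to 96.8% across the settings simulated.

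**4. How the covariate enters the model.** If pre and post scores are both responses and a covariate enters only as a main effect, it shifts both scores of a participant equally and cancels from the change. In simulated complete data sets, the group-by-time estimate and its SE were the same with and without it to six decimals. Covariate-by-time terms do act on the change, but that model matches regression of change on arm and covariate, so it does not obtain the gain in step 2.

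**5. A full prespecified list.** Site plus two covariates that prove non-prognostic:

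| r | 12-week score on arm, baseline, site, two covariates | Pre/post model with covariate-by-time terms |
|---|---|---|
| 0.3 | 0.84 | 1.02 |
| 0.5 | 0.90 | 1.02 |
| 0.7 | 0.96 | 1.02 |

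**The case against.** The strongest reply is that little depends on this. The adjusted estimate is additional, the unadjusted difference and its CI are reported regardless, Section 17 disclaims efficacy conclusions, and the results only help inform the next trial's power. All of that stands, and it caps the importance of the point.

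A second reply is that the largest gain, in step 2, comes from replacing the change-score model and would be available even without the imbalance clause. That is also right, so it is kept apart from step 3. The link to the rule is that it leaves the baseline value out in about 95% of trials. What is attributable to prespecifying some other covariate is smaller: about 2–3% of CI width at correlations of 0 to 0.2 with change. The documents support no particular correlation.

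A third is that if covariates enter a pre/post model as main effects only, neither the rule nor a prespecified list changes anything with complete data. True; the plan leaves this open, so the fix must name the model.

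A reader might infer that the rule biases the main comparison, inflates type I error, or always widens the interval. None of these is supported. The unadjusted estimate does not use the rule, simulated coverage stayed near 95%, and the rule's interval was wider or narrower than the unadjusted one depending on correlations that the documents do not give. Nor do the documents show that the R01 would be misplanned, since they do not say which estimate it will use.

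**Conclusion.** The point holds in a limited form. Selecting covariates by significant baseline imbalance leaves the adjusted estimate to chance: each variable enters about 5% of the time at an assumed 0.05 level. The cost is precision and reproducibility of a secondary estimate that may inform Aim 6.

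At 25 per arm, the recommended analysis has a CI about 16% / 10% / 4% narrower than the unadjusted change-score CI at pre-post correlation 0.3 / 0.5 / 0.7, a gain that is due to baseline adjustment. Under the rule that gain is under 1%. Separately, prespecifying one other covariate in place of the rule narrows the CI by about 2–3% at correlation 0 to 0.2 with change, 4% at 0.3 and 9% at 0.5. These sizes rest on the assumptions listed in the working; the direction does not change at 30 per arm. This is a worthwhile improvement that the investigators could make, with no consequence for the unadjusted result.

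**What to change.** In Section 9, Statistical Management and Analysis:

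- Delete the imbalance criterion. Define the adjusted estimate as the 12-week score regressed on arm, the outcome's baseline value and site, plus at most one or two already-collected variables judged prognostic and named before outcome data are seen. Use this list whatever the observed balance.
- Include site because it is the randomisation stratum, whatever the likelihood ratio test shows. That test can stay as a description of clustering.
- Do not offer the pre/post model with covariate-by-time terms as an equivalent. It reproduces a change-score regression and was about 2% wider than no adjustment with site and two non-prognostic covariates.
- Report baseline balance descriptively, without p-values.
- State whether the adjusted or the unadjusted estimate feeds the R01 power calculation.

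Cost: a few sentences and no new data. The downside is about 1% of CI width for each covariate that proves non-prognostic (1.011 for one, at 25 per arm), which is the reason to keep the list short.

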10. HUMAN SUBJECTS

The subject population will consist of 80 adults, 70-75 active-duty military personnel with chronic low back pain (CLBP) or chronic neck pain (CNP) and 5-10 yoga instructors or healthcare providers who have provided yoga or care for active-duty military personnel with CLBP or CNP.

In Phase 1:

30 qualitative interviews will be conducted. 20-25 active-duty military personnel and 5-10 yoga instructors or healthcare providers who have provided yoga or care for active-duty military personnel with CLBP or CNP will participate in the interviews. Inclusion criteria for the qualitative interviews includes being active-duty personnel in the U.S. military, and having a self-reported history of CLBP or CNP. Inclusion criteria for instructors/providers includes having self-reported experience teaching yoga or providing other pain treatments for active-duty military personnel with CLBP or CNP.

In Phase 2: 50 active-duty military personnel with CLBP will be recruited and randomized to either active hatha yoga or to restorative yoga. Inclusion criteria are as follows:

Inclusion:

- Diagnosis of CLBP or CNP > 6 months
- Willing to attend a yoga program for 12 weeks
- Willing to complete 3 assessments
- English literacy
- Have had no changes in pain treatments in the past month
- Willing to not change pain treatments during study unless medically necessary
- Have not practiced yoga more than 2x in the last 12 months

Exclusion:

- Back or neck surgery within the last year
- Back or neck pain due to specific systemic problem (e.g., lupus, scoliosis)
- Severe vertebral disk problems,
- Persistent sciatica or nerve compression > 3 months
- Coexisting chronic pain problem (e.g., migraine headaches, fibromyalgia)
- Serious or unstable psychiatric illness (e.g., psychosis, mania, episode, or substance dependence)
- Major coexisting medical illness (e.g., cancer, COPD, morbid obesity)
- Positive Romberg test (with or without sensory neuropathy)

No other exclusion criteria will be employed. No special classes of subjects or other vulnerable populations will be recruited. We will make efforts to recruit at least representative proportions of women and racial and ethnic minorities. More detail is provided on the inclusion of women and minorities document in this application.

